8.4. INFUSIONS

For babies meeting entry criteria, the first dose of cells/placebo will be infused intravenously as soon as possible. Infants will be pretreated with hydrocortisone, 1 mg/kg IV 30-60 minutes prior to each infusion if the subject was not on hydrocortisone for clinical purposes. The placebo group is receiving hydrocortisone to minimize the risk of infusion-related and/or allergic reaction to the placebo - the same risk minimization as for the active stem cell recipients. Cells/placebo will be infused over 10-20 minutes, followed by a saline flush ($\leq 5.0\text{mL}$) to clear the intravascular line. The study allows up to two doses of cells or placebo if the cell number is adequate from the cord blood unit. There must be a minimum of 8 hours between doses and both doses need to be completed by 48 hours post delivery. Babies receiving placebo infusions will be treated in an identical fashion to those receiving cells. The infusion product will be blinded to the hospital staff administering the cells and evaluating the babies' outcomes, as well as the family.

8.5. MONITORING DURING AND AFTER INFUSION

8.5.1. VITAL SIGNS

Vital signs will be assessed pre- infusion and for 15 minutes post infusion and per hospital routine thereafter.

8.5.2. METABOLIC STATUS

Daily chemistries are routinely obtained in infants with moderate to severe HIE when they are treated with hypothermia. Serum electrolytes, CBC, BUN, and creatinine, and frequently liver function tests are monitored at baseline, and then daily. We will record results of metabolic laboratories collected for clinical purposes during the cooling period and the first 24 hours post re-warming in the case report forms.

A Phase II Multi-site Study of Autologous Cord Blood Cells for Hypoxic Ischemic Encephalopathy (HIE) IND 14753 (BABYBAC II)

8.5.3. RESPIRATORY STATUS

A daily blood gas is standard in infants with moderate to severe HIE. Results from daily blood gases obtained for clinical purposes during cooling and for the first 24 hours after re-warming will be collected in the case report forms.

8.5.4. NEUROLOGIC STATUS

A neurological assessment will be performed at baseline, daily during cooling, and at discharge. This will be performed by a trained examiner.

8.5.5. HEMATOLOGIC STATUS

Monitoring of coagulation studies is considered routine for infants with HIE. PT/PTT results obtained for clinical purposes during cooling and for the first 24 hours after re-warming will be recorded in the case report forms.

8.5.6. FOLLOW UP VISITS

Subjects will return at one year (12 mo - 16 mo) corrected age. The following assessments will be recorded: History and physical exam, Bayley Scales of Infant Development III (BSID), neurological exam, adverse events and concomitant medications. Infants not testable on the BSID due to Cerebral Palsy, blindness or deafness will be assigned scores of 54, 46 and 46 respectively on the cognitive, language and motor of the BSID scale.

A Phase II Multi-site Study of Autologous Cord Blood Cells for Hypoxic Ischemic Encephalopathy (HIE) IND 14753 (BABYBAC II)

9. SCHEDULE OF EVENTS

	First Dose<40 hours postnatal if two doses are feasible <48 hours if only one dose is feasible	Second dose if feasible < 48 hours postnatal	Rewarming through postnatal day 21	Visit 1 12-16months
Screening	X			
Maternal consent or assent	X			
Collect UCB	X			
Labs ¹	X			
Blood Gas ²	X			
Neurological Assessment ³	X	X	X	X
Infusion and vitals ⁴	X	X (if cells are available)		
History and Physical Exam	X			X
Adverse events and concomitant meds	X	X	X	X
MRI			X	
PT/PTT ⁵	X		X	

¹ Serum Electrolytes, BUN, CBC, Creatinine, liver function obtained as part of routine care for HIE (section 8.5.2) ² Collected daily (section 8.5.3) ³ Collected at baseline, daily during cooling and prior to discharge (section 8.5.4) ⁴ Assessed pre-infusion and for 15min post infusion and per hospital SOC (section 8.5.1) ⁵ Collected during cooling and 24 hours after re-warming if obtained as part of routine care (section 8.5.5)
				

A Phase II Multi-site Study of Autologous Cord Blood Cells for Hypoxic Ischemic Encephalopathy (HIE) IND 14753 (BABYBAC II)

10. OTHER TREATMENTS/TESTS/CONCURRENT MEDICATIONS

Anti-seizure medication and sedation ideally will not be administered prior to hypothermia or study infusions, unless clinically indicated. All medications will be listed in concomitant medications in the case report forms.

11. PRIMARY OUTCOME MEASURES

11.1. BAYLEY SCALES OF INFANT AND TODDLER DEVELOPMENT- III

The Bayley Scales of Infant and Toddler Development-III (BSID) ²³ will be administered with all children at 12-16. Months corrected age. The Bayley-III is an individually-administered examination that assesses the current developmental functioning of infants and young children from birth to 42 months of age. This instrument has been shown to have adequate reliability and validity, and is considered the gold standard of infant and toddler assessment tools. The Bayley is a standardized, norm-referenced measure that assesses development in Cognitive, Language and Motor domains. Composite standard scores can be derived that have a mean of 100 and a standard deviation of 15.

All Bayley examiners for this study will be trained and certified to a criterion of 80% accuracy for administration and scoring. Certification will be completed via submission of a DVD of administration of the Bayley-III Scales with a non-study child of the target age for the study. The DVD will be reviewed and the accuracy of administration and scoring will be determined by the study gold standard examiner within two weeks of submission of the DVD. Additional DVDs will be submitted by the examiner until the criterion of 80% accuracy is reached for both administration and scoring. Each examiner must be certified once per year. No study participants may be assessed by an examiner who has not been certified.

For children with sensory impairments, an attempt should be made to administer Bayley items and a decision about validity of assessment will be made subsequently with consultation with the gold standard Bayley examiner. However, some children with sensory impairment cannot be reliably assessed with the Bayley-III. This includes children who are: 1) legally blind (< 20/200 with glasses). 2) Hearing impaired and have no amplification/hearing aids. If a child does have hearing aids, the Bayley must be completed with the hearing aids in place. If the child has profound hearing loss and is expected to undergo a cochlear implant, the child will not be able to be tested. 3) Child is both vision and hearing impaired (Deaf/Blind). These children cannot be tested with the Bayley. Infants not testable on BSID due to CP, blindness or deafness be assigned respective scores of 54, 46 and 46 on the cognitive, language and motor components of the BSID III.

A Phase II Multi-site Study of Autologous Cord Blood Cells for Hypoxic Ischemic Encephalopathy (HIE) IND 14753 (BABYBAC II)

Non-English language learners will be assessed by a bilingual examiner who has been certified or with the assistance of a qualified interpreter. Interpreters must be instructed to translate the Bayley instructions to the child verbatim and to not repeat instructions unless instructed to do so by the examiner. Language scores will not be derived for non-English language learners as the normative developmental progression of language milestones in other languages may not be accurately reflected on the Bayley Language Scales.

11.2.MRI

An MRI is routinely obtained on HIE infants between 7 – 28 postnatal days. Ideally the MRI will be done optimally at 10 days of life (but with an acceptable window between 7 days and 21 days of life as suggested by the 2014 revised guidelines for infants with HIE, to assess extent of injury) ²¹. Results from the standard of care MRI will recorded for the study.

11.3.NICU DISCHARGE

Tracking information will be recorded at discharge, and will include phone numbers and home address. All surviving infants will be followed for one year for the in-person assessment.

An attempt will be made at each site to obtain an autopsy in case of death both prior to and following NICU discharge. Autopsy results, if available, will be included in the case report forms.

11.4. SHORT TERM/HOSPITAL OUTCOMES/STUDY ENDPOINT

Short term outcomes will be considered secondary outcomes for the study. We will compare adverse outcomes, including mortality, seizures, need for nitric oxide and need for ECMO, need for G-tube feeding at discharge, and discharge on anti-epileptic medications. This information will be collected in case report forms.

11.5.LONG TERM OUTCOMES/PRIMARY OUTCOME/STUDY ENDPOINT

The Primary outcome of the study will be survival at one year with Bayley III scores in all three domains ≥ 85 .

12. RISKS AND BENEFITS

12.1.RISK AND BENEFITS OF STUDY

Infusion of a neonate's own cord blood cells during routine cooling is hoped to improve survival and neurological outcome as compared to infants that are only cooled and receive red blood cells. Autologous cells should eliminate any risk of graft vs host reaction. If cord blood cells are collected and not infused, cord blood cells will be cryopreserved for later autologous use for the subject. Complications of cord blood infusions could include infection, volume overload, hypertension, allergic or anaphylactic reactions, hyperviscosity or pulmonary edema and will be

A Phase II Multi-site Study of Autologous Cord Blood Cells for Hypoxic Ischemic Encephalopathy (HIE) IND 14753 (BABYBAC II)

monitored during and after infusion. The medication hydrocortisone given prior to the infusions may increase blood sugar, blood pressure and fluid retention.

13. SAFETY AND ADVERSE EVENT REPORTING

Adverse Events (AE) Adverse events and serious adverse events parameters are listed below. The parameters for events are derived from prior studies of thawed/washed cord blood cells used for allogeneic transplant, in combination with expected physiologic responses to therapeutic hypothermia, which by definition and inclusion criteria, will be concurrently underway when the study infusions are administered. The physiologic response to hypothermia leads to decreased heart rate during cooling (the mean Heart Rate during cooling in the NICHD NRN pivotal trial was 109); therefore a lower level to define significant bradycardia is used (Shankaran 2005). Other AE/SAE definitions are taken from the NICHD Optimizing cooling trial, to account for the concurrent use of therapeutic hypothermia, and the AE/SAE category definitions developed for the NICHD Pediatric Trials Network (Shankaran 2014 ;England 2016). Definitions for each AE parameter are listed in MOP-01 Section 10.1.

SAEs may include:

- Acidosis
- Allergic reaction/hypersensitivity
- GI Pathology
- Hemoglobinuria
- Hyperglycemia
- Hypoglycemia
- Hypertension
- Hypotension, and fever in the absence of neutropenia
- Hypoxia
- Infectious Disease
- Polycythemia
- Pulmonary Hypertension, within the first 24 hours
- Sinus bradycardia
- Sinus tachycardia
- Dyspnea
- Any other cardiac rhythm disturbances,
- Any other reported SAE, including death

A Phase II Multi-site Study of Autologous Cord Blood Cells for Hypoxic Ischemic Encephalopathy (HIE) IND 14753 (BABYBAC II)

13.1.1. ADVERSE EVENTS (AE)

Adverse event means any untoward medical occurrence associated with the use of the investigational product, whether or not considered related to the investigational product.

13.1.2. SERIOUS ADVERSE EVENTS (SAE)

An adverse event or suspected adverse reaction is considered “serious” if, in the view of either the investigator or sponsor, it results in any of the following outcomes: death, a life-threatening adverse event, inpatient hospitalization or prolongation of existing hospitalization, a persistent or significant incapacity or substantial disruption of the ability to conduct normal life functions, or a congenital anomaly/birth defect. Important medical events that may not result in death, be life-threatening, or require hospitalization may be considered serious when, based upon appropriate medical judgment, they may jeopardize the patient or subject and may require medical or surgical intervention to prevent one of the outcomes listed in this definition.

13.1.3. GRADE/SEVERITY

Grade/Severity will be performed per CTCAE guidelines.

13.1.4. SUSPECTED ADVERSE REACTION

Suspected adverse reaction means any adverse event for which there is a reasonable possibility that the investigational product caused the adverse event. ‘Reasonable possibility’ means there is evidence to suggest a causal relationship between the investigational product and the adverse event.

13.1.5. CAUSALITY

The Investigator will use the following question when assessing causality of an adverse event to the investigational product: Is there a reasonable possibility that the drug caused the event? An affirmative answer designates the event as a suspected adverse reaction.

13.2. ADVERSE EVENT REPORTING

All adverse events reported or observed during the study beginning at the time of the autologous cord blood infusion must be recorded and maintained in the study participant’s paper files or electronic case report forms. Information to be reported includes when the site became aware of the event, investigator-specified assessment of severity and relationship to study therapy, whether there is an alternative etiology, seriousness, as well as any required treatment or evaluations, and outcome. In general, investigators should report adverse events as diseases or syndromes whenever possible, instead of reporting individual component symptoms, signs, laboratory abnormalities, and sequelae.

A Phase II Multi-site Study of Autologous Cord Blood Cells for Hypoxic Ischemic Encephalopathy (HIE) IND 14753 (BABYBAC II)

Severe adverse reactions (fatal or life threatening) that are unexpected and related will be reported to the FDA by Duke University within seven calendar days of receipt of the information by telephone, mail or fax, following FDA guidelines. All non-life threatening serious, related, and unexpected adverse events will be reported to the FDA via a written report within 15 days of receipt of the information (21 CFR 312.32) by Duke University. If the principal investigator assesses the event to be unrelated to the study, then the event will not require expedited reporting but will be included in a summary report.

Investigators are requested to notify the Principle Investigators at Duke University within 24 hours of all SAEs. The Principal Investigator or Sub-Investigator at each site is responsible for informing their Institutional Review Board (IRB). Copies of SAE correspondence with all Principal Investigators or Sub-Investigators, governing authorities, ethics committees, and the sponsor must be submitted to Duke University for filing.

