In keeping with the Bayesian nature of the trial design, we will use a Bayesian interim monitoring approach to determine whether systematic differences are emergent among the two treatment groups in the incidence of any of the adverse events listed above. Specifically, after every 40 babies enrolled in the trial have spent 24 hours post their final study transfusion, we will calculate the posterior probability that one group has higher incidence of any adverse events than another. In statistical terms, the treatment will be considered harmful (i.e., the DSMC may consider termination of the trial) if for a pre-specified threshold η , the posterior probability of treatment harm (in terms of the above adverse events) is greater than η ; in other words if the predictive probability $P(\theta > 1 | X) > \eta$, where θ denotes the relative risk favoring the treatment group and X is the data available. In order to allow for a liberal safety monitoring regime to ensure patient safety, we propose to take $\eta = 80\%$. However, we will also present the 95% credible interval for θ , as well as the entire posterior distribution for θ in a graphical fashion to the DSMC so that they have a full appreciation for the range of possible values of θ . All interim analyses will adjust for baseline level of encephalopathy, the stratification variable for this trial, whenever computationally feasible.

The choice of a prior distribution is essential and controversial in Bayesian analyses. Thus, we can compute the posterior probability of treatment harm and the posterior distribution of the associated relative risk under two sets of priors – (a) a non-informative prior that does not assume any substantive prior information about treatment differences in terms of the adverse events listed above, and (b) an informative prior based on treatment differences for these adverse events observed in the Phase I trial. However, we realize that the standard Bayesian approach of running the analysis with different priors provides only a partial solution, as the results on stopping are often inconclusive, especially when few data have accumulated. Instead of worrying about the selection of a single correct prior, we will also explore the use of a robust Bayesian approach which replaces a prior distribution with a class of priors and calculates the corresponding posterior probabilities for decision making²⁶.

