15.3. STATISTICAL ANALYSIS PLAN

All statistical analyses, including interim monitoring, will be conducted using the intent to treat principle, unless explicitly specified otherwise for certain secondary and/or post-hoc analyses. A Bayesian approach will be used for conducting the primary analysis in this trial. We propose to apply a log-binomial regression model and a neutral prior that will be centered at RR=1.0 to final

A Phase II Multi-site Study of Autologous Cord Blood Cells for Hypoxic Ischemic Encephalopathy (HIE) IND 14753 (BABYBAC II)

efficacy and safety data, where final data is defined as data contained in the study database after database lock. Database lock will occur either after 160 infants have completed the study or the study is terminated early for efficacy, futility, or safety. In addition to using a neutral prior, final analyses on locked data and some interim analyses will develop posterior distributions using skeptical (centered at $RR = 1.1$) priors and/or enthusiastic (centered at $RR = 0.625$) priors as well. In all analyses, MCMC methods will be used to sample from the Posterior distribution.

All analyses will involve estimating a Posterior distribution based on a log-binomial regression model with covariates and MCMC methods. In addition to estimating the treatment effect on the log relative risk scale, the log-binomial regression will adjust for level of encephalopathy. For the intercept and the encephalopathy terms, Normal (mean = 0, sd=100) priors will be used. For the term representing the log relative risk, skeptical, neutral, and enthusiastic priors will be used to estimate posterior distributions for the relative risk.

With respect to the primary efficacy endpoint, the estimated Posterior distribution of relative risk based on the data and the neutral prior will be used to determine posterior probabilities of >0 , >10 and $>20\%$ decrease in death or moderate/severe disability, as well as graphical displays of the Posterior distribution and appropriate 95% credible intervals for the relative risk. In addition to adjusting for level of encephalopathy and center in the log-binomial model, the final analysis of efficacy will also perform sensitivity analyses concerning possible treatment effect confounders present at randomization. All additional covariates added to the model will utilize Normal (mean=0, sd=100) priors.

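### Adverse event recording starts at the infusion, so randomised infants never infused, and the interval after the first hydrocortisone dose, fall outside it although safety is analysed by intent to treat

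*Combined protocol and SAP*

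**What the plan says.** **Recording.** Section 13.2 fixes the start: "All adverse events reported or observed during the study beginning at the time of the autologous cord blood infusion must be recorded". It gives no other starting point. Collection then continues well past the infusions. The schedule in section 9 marks adverse events at both doses, from rewarming to postnatal day 21, and at 12-16 months. Section 8.5.6 lists "neurological exam, adverse events and concomitant medications" at that last visit.

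**Analysis.** Section 15.3 states: "All statistical analyses, including interim monitoring, will be conducted using the intent to treat principle". Exceptions are allowed only where explicitly specified for certain secondary or post-hoc analyses. The final model is applied to "efficacy and safety data, where final data is defined as data contained in the study database after database lock".

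**From randomisation to infusion.** Section 7.1.3 randomises after consent. Section 8.1 describes cell preparation as following allocation, and withholds cells or placebo if the Gram stain is positive. Section 8.4 adds: "Infants will be pretreated with hydrocortisone, 1 mg/kg IV 30-60 minutes prior to each infusion". This applies in both arms unless the infant already receives the drug for clinical reasons. Section 12.1 says that hydrocortisone "may increase blood sugar, blood pressure and fluid retention". Hyperglycemia and hypertension are on the list of monitored events in section 13.4.

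**Interim comparison.** Section 13.4 concentrates on events within 24 hours of infusion and schedules a look each time a further 40 enrolled infants "have spent 24 hours post their final study transfusion". Section 8.4 allows one or two infusions, at least 8 hours apart and both completed by 48 hours after delivery.

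**The concern.** The population to be analysed is everyone randomised, but the rule that generates the safety data begins at a later event that some randomised infants may never reach. For those infants the plan gives neither a start of recording nor a comparison window, and does not say how they are coded.

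The same start point leaves out the first part of a study procedure. Hydrocortisone is given because of the trial, two of its stated risks match listed safety events, and the time between the first dose and the first infusion is not covered.

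A related question concerns the interim window. If each infusion opens its own 24 hours, the time at risk depends on the number of infusions, which is settled after randomisation. At stake are a complete safety record and a harm relative risk that reflects the product and not the length of observation.

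**Working it through.** The documents give no figure that depends on these rules, so there is nothing to reproduce. The core of the point comes from setting the sections side by side. The arithmetic below is illustrative, and its inputs are assumptions unless a section is cited.

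**1. Never-infused infants.** Randomisation (7.1.3) precedes the Gram stain of the product (8.1), so an infant can be randomised and not infused. Inclusion criterion 2 (able to receive at least one dose before 48 hours of age) does not prevent this, because the stain comes later. Such an infant has no start under 13.2, no window under 13.4, and cannot satisfy the look trigger in 13.4. Two treatments remain: exclusion, which conflicts with 15.3, or inclusion with no observed events. The number of such infants is not given. If 2-10% of 160 were affected, that is 160 × 0.02 = 3.2 to 160 × 0.10 = 16 infants.

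**2. Hydrocortisone.** The uncovered time is the 30-60 minutes before the first infusion (8.4). Pretreatment for a second infusion falls after the first infusion and so within recording.

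**3. Length of the interim window.** One infusion gives 24 hours. If each of two infusions opens 24 hours, the combined window is 24 + gap: 24 + 8 = 32 hours at the minimum gap, and 24 + 24 = 48 hours once the gap reaches 24 hours.

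**4. What the longer window does to one infant's risk.** Assume a constant hazard and a 24-hour risk p of at least one composite event. Over w hours the risk is 1 − (1 − p)^(w/24).

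| p (assumed) | 32 h risk | ratio to p | 48 h risk | ratio to p |
|---|---|---|---|---|
| 0.1 | 0.131 | 1.31 | 0.190 | 1.90 |
| 0.3 | 0.378 | 1.26 | 0.510 | 1.70 |
| 0.5 | 0.603 | 1.21 | 0.750 | 1.50 |

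**5. What it does to the arm comparison.** With share s given two infusions, an arm's risk is s × (risk over w) + (1 − s) × p. Take p = 0.3 and no treatment effect.

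- Equal shares (70% in both arms): relative risk 1.00.
- 70% cells, 100% placebo, 32 h: (0.7 × 0.378 + 0.3 × 0.3) / 0.378 = 0.94. At 48 h: (0.7 × 0.51 + 0.3 × 0.3) / 0.51 = 0.88.
- 100% cells, 70% placebo: 1.07 at 32 h and 1.14 at 48 h.

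The 80% posterior harm rule was simulated at a single look with 80 per arm (Jeffreys beta priors, no adjustment for encephalopathy). It fires about 20% of the time with equal shares, 13% to 5% in the second case and 30% to 48% in the third. Bias therefore needs unequal shares and could go either way.

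**6. Price of a longer monitored window.** Suppose the true 24-hour relative risk is 1.5 and a further 24 hours of equal background hazard is added to both arms. With placebo risk 0.30: (1 − 0.55 × 0.70) / (1 − 0.70²) = 0.615 / 0.51 = 1.21. With placebo risk 0.50: (1 − 0.25 × 0.50) / (1 − 0.50²) = 0.875 / 0.75 = 1.17. Replacing the post-infusion composite with a longer window would dilute the signal that it is meant to detect.

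**The case against.** The strongest reply is that both arms are handled alike. Section 8.4 ties the number of doses in either arm to the cord blood unit and requires identical treatment of placebo infants, and the Gram stain rule covers both products. Both arms receive hydrocortisone. Pre-infusion vital signs are assessed (8.5.1), clinical laboratory results during cooling go into the case report form (8.5.2), and a raised glucose or pressure that persists into the infusion is recorded. Event definitions sit in a manual of procedures that is not among the documents. Most of this stands, and it limits the point to completeness and definition. It does not supply a start of recording for an infant who is never infused, and a laboratory value on file is not an adverse event record.

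A reader might infer more than the text supports:

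- *That adverse events are collected only over a window set by the number of infusions.* Collection runs to 12-16 months. Only the interim comparison is tied to infusion, and the 24 hours after the final infusion is the trigger for a look, not an event window.
- *That never-infused infants enter as event-free.* The documents do not say so; exclusion is equally possible.
- *That a low cell count leads to no infusion.* Section 8.1 uses the count to choose between one and two doses, and does not mention none.
- *That the harm relative risk is biased.* If 5-20% of the cell arm alone were never infused and counted as event-free, a true 1.5 would read 1.5 × 0.95 = 1.43 to 1.5 × 0.80 = 1.20. With equal non-infusion it stays at 1.5. Section 8.1 describes counting only for processed cells, and section 8.2 makes placebo from unprocessed blood, so which count sets the number of placebo doses is unclear. That does not show that the arms differ.

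**Conclusion.** The mismatch is real and rests on the text alone. Recording starts at the infusion, the analysis population is all randomised infants, and a randomised infant may never be infused. Onsets between the first hydrocortisone dose and the first infusion are likewise outside recording. Because both arms receive hydrocortisone, this second gap concerns complete safety capture and not bias between arms.

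The interim window is ambiguous: the text does not say whether it runs from the first, the last or each infusion. Under the last of these readings it is 24 hours for one infusion and 32-48 hours for two. It distorts the harm relative risk only if the share with two infusions differs by arm.

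The effect on that relative risk cannot be quantified from the documents, which give no event rates, no two-infusion shares and no non-infusion rate. It may be small. The point should be addressed because the correction is cheap and safety is part of the primary objective in section 4.

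**What to change.** 1. In section 13.2, start adverse event recording at randomisation in both arms, with the matching start time in the case report form, so that every randomised infant has recorded safety data.
2. In section 13.4, keep the 24-hour post-infusion comparison as the focus for infusion-related harm, but define it at one length for every infused infant, for example 24 hours from the first infusion. That choice leaves at most 24 − 8 = 16 hours after a second infusion, so events in the 24 hours after a second infusion should be tabulated separately.
3. Add a supporting intent-to-treat summary from randomisation over a common window for all randomised infants. State how never-infused infants enter each analysis and how they count towards each group of 40.

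A longer window from randomisation should not replace the post-infusion composite, because of the dilution to about 1.2 shown in step 6 of the working.

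The cost is a changed start time on the form, one sentence in 13.2, a short definition in 13.4 and one added table. The downside is that more background events of HIE and cooling will be recorded. No treatment changes.
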